11.4 Recording of Data

A CRF is required and must be completed for each subject by qualified and authorized personnel. All data on the CRF must reflect the corresponding source document, except when a section of the CRF itself is used as the source document. Any correction to entries made on the CRF must be documented in a valid audit trail where the correction is dated, the individual making the correction is identified, the reason for the change is stated, and the original data are not obscured. Only data required by the protocol for the purposes of the study should be collected.

The investigator must sign each CRF. The investigator will report the CRFs to the sponsor and retain a copy of the CRFs.

11.5 Identification of Source Data

All data to be recorded on the CRF must reflect the corresponding source documents. For the following item(s), the data recorded directly on the CRF are to be considered source data:

- Study drug compliance (eg, the reason for any change of dosage)
- Indication for prior/concomitant medication (drug/therapy)
- Discontinuation information (eg, in the case of lost to follow-up due to the subject choice)
- Sampling date and time for the drug concentration
- Sampling date for the clinical laboratory tests
- Comments and other information on AEs (eg, severity, relationship to study drug, outcome)

11.6 Retention of Records

The circumstances of completion or termination of the study notwithstanding, the investigator (or if regionally required, the head of the medical institution or the designated representative) is responsible for retaining all study documents, including but not limited to the protocol, copies of CRFs, the Investigator's Brochure, and regulatory agency registration documents (eg, Form FDA 1572, ICFs, and IRB/IEC correspondence). The site should plan to retain study documents, as directed by the sponsor, for at least 2 years after the last approval of a marketing application in an ICH region and until there are no pending or contemplated marketing applications in an ICH region or at least 3 years have elapsed since the formal discontinuation of clinical development of the investigational product.

It is requested that at the completion of the required retention period, or should the investigator retire or relocate, the investigator contact the sponsor, allowing the sponsor the option of permanently retaining the study records.

11.7 Auditing Procedures and Inspection

In addition to routine monitoring procedures, the sponsor's Clinical Quality Assurance department conducts audits of clinical research activities in accordance with the sponsor's SOPs to evaluate compliance with the principles of ICH GCP and all applicable local regulations. If a government regulatory authority requests an inspection during the study or after its completion, the investigator must inform the sponsor immediately.

11.8 Handling of Study Drug

All study drug will be supplied to the PI (or a designated pharmacist) by the sponsor. Drug supplies must be kept in an appropriate secure area (eg, locked cabinet) and stored according to the conditions specified on the drug labels. The investigator (or a designated pharmacist) must maintain an accurate record of the shipment and dispensing of the study drug in a drug accountability ledger, a copy of which must be given to the sponsor at the end of the study. An accurate record of the date and amount of study drug dispensed to each subject must be available for inspection at any time. The CRA will visit the site and review these documents along with all other study conduct documents at appropriate intervals once study drug has been received by the site.

All drug supplies are to be used only for this study and not for any other purpose. The investigator (or site personnel) must not destroy any drug labels or any partly used or unused drug supply before approval to do so by the sponsor. At the conclusion of the study and as appropriate during the study, the investigator (or a designated pharmacist) will return all used and unused drug containers, drug labels, and a copy of the completed drug disposition form to the sponsor's CRA (or designated contractor) or, when approval is given by the sponsor, will destroy supplies and containers at the site.

11.9 Publication of Results

All manuscripts, abstracts, or other modes of presentation arising from the results of the study must be reviewed and approved in writing by the sponsor in advance of submission pursuant to the terms and conditions set forth in the executed Clinical Trial Agreement between the sponsor/CRO and the institution/investigator. The review is aimed at protecting the sponsor's proprietary information existing either at the date of the commencement of the study or generated during the study.

The detailed obligations regarding the publication of any data, material results, or other information generated or created in relation to the study shall be set out in the agreement between each investigator and the sponsor or CRO, as appropriate.

11.10 Disclosure and Confidentiality

The contents of this protocol and any amendments and results obtained during the study should be kept confidential by the investigator, the investigator's staff, and the IRB/IEC and will not be disclosed in whole or in part to others, or used for any purpose other than reviewing or performing the study, without the written consent of the sponsor. No data collected as part of this study will be used in any written work, including publications, without the written consent of the sponsor. These obligations of confidentiality and non-use shall in no way diminish such obligations as set forth in either the Confidentiality Agreement or Clinical Trial Agreement executed between the sponsor/CRO and the institution/investigator.

All persons assisting in the performance of this study must be bound by the obligations of confidentiality and non-use set forth in either the Confidentiality Agreement or Clinical Trial Agreement executed between the institution/investigator and the sponsor/CRO.

11.11 Discontinuation of Study

The sponsor reserves the right to discontinue the study for medical reasons or any other reason at any time. If a study is prematurely terminated or suspended, the sponsor will promptly inform the investigators/institutions and regulatory authorities of the termination or suspension and the reason(s) for the termination or suspension. The IRB/IEC will also be informed promptly and provided the reason(s) for the termination or suspension by the sponsor or by the investigator/institution, as specified by the applicable regulatory requirement(s).

The investigator reserves the right to discontinue the study should his/her judgment so dictate. If the investigator terminates or suspends a study without prior agreement of the sponsor, the investigator should inform the institution where applicable, and the investigator/institution should promptly inform the sponsor and the IRB/IEC and provide the sponsor and the IRB/IEC with a detailed written explanation of the termination or suspension. Study records must be retained as noted above.

11.12 Subject Insurance and Indemnity

The sponsor will provide insurance for any subjects participating in the study in accordance with all applicable laws and regulations.

12 APPENDICES

Appendix 1 Immune-related Response Evaluation Criteria in Solid Tumors

Investigators should follow the guidelines provided here which are an adaptation of RECIST 1.1 and irRC. The following guide represents a summary of irRECIST and is meant to help investigators in providing more objective and reproducible immune therapy related tumor response assessments in solid tumors.

The key changes for irRECIST are:

- IrRECIST allows the site to select up to ten (10) target lesions at baseline, five (5) per organ, if clinically relevant via CT/MRI scans or by electronic calipers for skin lesions. The ability to continue treatment, if clinically stable, until repeat imaging scans ≥ 4 weeks later (in most cases at the next scanning time point 6 weeks later) to confirm immune-related progressive disease (irPD)

irRECIST Lexicon	
1. Baseline Assessments	
Measurable (Target) lesions	
Measurable lesions must be accurately measured in at least one dimension with a minimum size of:
 
 • 10 mm in the longest diameter (LDi) by CT or MRI scan (or no less than double the slice thickness) for non-nodal lesions and ≥ 15 mm in short axis (SDi) for nodal lesions • 10 mm in LDi for clinical lesions (must be measured using electronic calipers) • Identify up to 10 lesions, not more than 5 from one organ system. Lymph nodes are considered one organ system • Likely to be reproducible across all time points • Representative of tumor burden • May include lesions in previously irradiated areas ONLY if there is demonstrated progression in that lesion after irradiation • Sum of diameters (SOD) of all target lesions including nodal and non-nodal are reported as baseline SOD, which is used for assessing tumor response at follow-up time points
Bone lesions	
Regardless of the imaging modality, blastic bone lesions will not be selected as target lesions. Lytic or mixed lytic-blastic lesions with a measurable soft tissue component ≥ 10 mm can be selected as target lesions.

Cystic and Necrotic Lesions as Target Lesions	
Lesions that are partially cystic or necrotic can be selected as target lesions. The LDi of such a lesion will be added to the SOD of all target lesions at baseline. If other lesions with a nonliquid/nonnecrotic component are present, those should be preferred.

Lesions with Prior Local Treatment	During target lesion selection the radiologist will consider information on the anatomical sites of previous intervention (eg, previous irradiation, RF-ablation, TACE, surgery). Lesions undergoing prior intervention will not be selected as target lesions unless there has been a demonstration of progression in the lesion.
Nonmeasurable (Nontarget) lesions	
Nontarget lesions will include:
 
 • Measurable lesions not selected as target lesions. There is no limit to the number of nontarget lesions that can be recorded at baseline • Other types of lesions that are confidently felt to represent neoplastic tissue, but are difficult to measure in a reproducible manner. These include bone metastases, leptomeningeal metastases, malignant ascites, pleural or pericardial effusions, ascites, inflammatory breast disease, lymphangitis cutis/pulmonis, cystic lesions, ill-defined abdominal masses, etc. • Multiple non target lesions from the same organ may be captured as a single item on the eCRF (eg, multiple liver metastases) 
Nontarget lesions should be reported as present at baseline

SOD_{baseline}	Sum of diameters at baseline = LDi of all non-nodal + SDi of all nodal target lesions
2. Time point Assessments After Baseline	
Target lesion measurements	
Locate image that optimizes the LDi of the non-nodal target lesion or SDi of target node(s). There is no need to go to an identical slice from baseline.
 
Measure the respective LDi and SDi for all target lesions and calculate time point SOD (SOD_{timepoint}).
 
Special consideration for target lesions:
 
 • If target lesion is too small to measure, a default value of 5mm should be entered on eCRF. • If target lesion is 5-10mm, actual diameter should be entered in the eCRF. • If target lesion splits into 2 or more lesion then the LDi of split lesions will be added and entered in place of that lesion. • If two target lesion merged to form one lesion than LDi of one should be entered as “0mm” while the other lesion should have the diameter of the merged lesion.
Nontarget Lesion Assessment	Nontarget lesions are evaluated qualitatively as present, absent, not evaluable (NE) or unequivocal progression. The response of nontarget lesions primarily contributes to the overall response assessments of irCR. Nontarget lesions do not affect irPR and irSD assessments. Only a massive and unequivocal worsening of nontarget lesions alone, even in the presence of stable disease or a partial response in the target lesion is

	indicative of irPD. IrCR is not possible unless all nontarget lesions are absent.
Definition of New Lesion	
Any lesion that was not recorded at baseline. There is no minimum size criteria to identify a new lesion and clinical judgment must be used by the PI.
 
 • May include a lesion in an anatomical location that was not scanned at baseline (ie, brain) • Should be unequivocal and not due to differences in scanning technique • If equivocal, should be assessed at next time point; if present, irPD is the date the lesion was first seen (not the date confirmed)
3. irRECIST Overall Tumor Assessment	
irCR	
 • Complete disappearance of all measurable and nonmeasurable lesions (from baseline) and there are no unequivocal new lesions (unconfirmed irCR). • Lymph nodes must decrease to <10 mm in SDi. • Confirmation of response is required ≥ 4 weeks later, preferably at next time point, to be considered a confirmed irCR.
irPR	
 • If the SOD_{timepoint} of TLs decreases by ≥ 30 % compared to SOD_{baseline} and there are no unequivocal new lesions, and no progression of nontarget disease, it is an irPR (unconfirmed). • Confirmation is required ≥ 4 weeks later, preferably at next time point, to be considered a confirmed irPR.
irSD	
Failure to meet criteria for irCR or irPR in the absence of irPD.
 
 • If the sum of the TLs and the status of the nontarget lesions do not reach the criteria to meet irPR or irPD (increase $\geq 20\%$ and at least 5 mm absolute increase in SOD compared to nadir[†]) the response is irSD. • irSD = neither 30% decrease compared to SOD_{baseline} or 20% increase and at least 5 mm absolute change compared to nadir. • [†]SOD_{nadir}: Lowest measure SOD of TLs at any time point from baseline onward.
irPD	
Minimum 20% increase and a minimum 5 mm absolute increase in SOD compared to nadir, or irPD for nontarget lesion(s) or unequivocal new lesion(s).
 
 • Confirmation of progression is recommended at a minimum of 4 weeks after the first irPD assessment (preferably at next tumor assessment time point). 
The decision to continue study treatment after the first evidence of PD is at the investigator's discretion based on the clinical status of the subject as described in table below

	Clinically Stable		Clinically Unstable	
	Imaging	Treatment	Imaging	Treatment
1st radiologic evidence of PD	Repeat imaging at ≥ 4 weeks (next TA time point) to confirm PD	May continue study treatment at the Investigator's discretion while awaiting confirmatory scans	Repeat imaging at ≥ 4 weeks to confirm PD per physician discretion only	Discontinue treatment
Subsequent scan confirms PD	No additional imaging required	Discontinue treatment	No additional imaging required	N/A
Subsequent scan shows SD, PR or CR	Continue regularly scheduled imaging assessments	Continue study treatment at the Investigator's discretion	Continue regularly scheduled imaging assessments	May restart study treatment if condition has improved and/or clinically stable per investigator's discretion

Subjects may continue receiving study treatment while waiting for confirmation of irPD if they are clinically stable as defined by the following criteria:
 
 • Absence of signs and symptoms (including worsening of laboratory values) indicating disease progression • No decline in ECOG performance status • Absence of rapid progression of disease • Absence of progressive tumor at critical anatomical sites (eg, cord compression) requiring urgent alternative medical intervention 
If irPD is confirmed and the subject is experiencing extraordinary clinical benefit, site must contact sponsor to discuss continuing treatment
				
irNE	Used in exceptional cases where insufficient data exists due to poor quality of scans or missed scans or procedure			

Derivation of irRECIST overall responses			
Measurable response	Non-measurable response		
Target Lesions (% change in SOD)^a	Nontarget Lesions Status	New Lesions Status	Overall Response (irRECIST)
↓100	Absent	Absent	irCR ^b
↓100	Present/NE	Absent	irPR ^b
↓ ≥ 30	Present/Absent/NE	Absent	irPR ^b

↓<30 to <20↑	Present/Absent/NE	Absent	irSD
↓100 ↓≥30 ↓<30 to <20↑ NE	Present/Absent/NE	Present	irPD ^b
↓100 ↓≥30 ↓<30 to <20↑ NE	Unequivocal progression	Any	irPD ^b
↑≥20 from nadir	Any	Any	irPD ^b
NE	Present/Absent/NE	Absent	irNE ^b

irCR = immune-related complete response, irNE = immune-related not evaluable, irPD = immune-related progression disease, ir PR = immune-related partial response, irSD = immune-related stable disease, NE = Not evaluable, irRECIST = immune-related Response Evaluation Criteria in Solid Tumors SOD = sum of diameters

a: Decreases assessed relative to baseline, including measurable lesions only.

b: Assuming response (irCR) and progression (irPD) are confirmed by a second, consecutive assessment at least 4 weeks apart.

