If the subject did not have a post-baseline tumor assessment, or the subject only had one post-baseline tumor assessment of an early SD (duration < 5 weeks) as the overall response, or post-baseline tumor assessments are not evaluable (i.e. recorded as 'NE' as overall responses via the CRF, maybe due to missing anatomy or poor image quality), then BOR = NE.

- **SD**

If the BOR is not a confirmed CR/PR, NE, Unknown or PD, then the BOR is stable disease (SD).

Table 4 General Rules Deriving BOR per irRECIST

Timepoint 1 Overall Response	Timepoint 2 (\geq 4 weeks since Timepoint 1) Overall Response	BOR
CR	CR	CR
CR	PR	SD if duration of SD \geq 5 weeks, otherwise PD
CR	SD	SD if duration of SD \geq 5 weeks, otherwise PD
CR	PD	SD if duration of SD \geq 5 weeks, otherwise PD
CR	NE	SD if duration of SD \geq 5 weeks, otherwise NE. In the special case, if CR is at the next timepoint after NE, BOR will be CR.
CR ^a		SD if duration of SD \geq 5 weeks, otherwise NE
PR	CR ^b	PR
PR	PR	PR
PR	SD	SD. In the special case if PR or CR is at the next timepoint after SD, BOR will be PR.
PR	PD	SD if duration of SD \geq 5 weeks, otherwise PD
PR	NE	SD if duration of SD \geq 5 weeks, otherwise NE. In the special case, if PR or CR is at the next timepoint after NE, BOR will be PR.
PR ^a		SD if duration of SD \geq 5 weeks, otherwise NE
SD	CR ^b	SD
SD	PR ^b	SD
SD	SD	SD
SD	PD	SD if duration of SD \geq 5 weeks, otherwise PD
SD	NE	SD if duration of SD \geq 5 weeks, otherwise NE
SD ^a		SD if duration of SD \geq 5 weeks, otherwise NE
PD	CR ^b	SD if duration of SD \geq 5 weeks, otherwise PD
PD	PR ^b	SD if duration of SD \geq 5 weeks, otherwise PD
PD	SD	SD if duration of SD \geq 5 weeks, otherwise PD
PD	PD	PD

PD	NE	PD
PD ^a		PD
NE	NE	NE
UNK	UNK	UNK (Unknown) if there was no a baseline tumor assessment.

^a If this was the only tumor response assessment (e.g. study treatment was discontinued). ^b The subject should be followed for ≥ 4 weeks to confirm the CR/PR.

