Nontarget Lesion Assessment	Nontarget lesions are evaluated qualitatively as present, absent, not evaluable (NE) or unequivocal progression. The response of nontarget lesions primarily contributes to the overall response assessments of CR. Nontarget lesions do not affect PR and SD assessments. Only a massive and unequivocal worsening of nontarget lesions alone, even in the presence of stable disease or a partial response in the target lesion is indicative of PD. CR is not possible unless all non-target lesions are absent.
Definition of New lesion	Any lesion which was not recorded at baseline. There is no minimum size criteria to identify a new lesion and clinical judgment must be used by the PI. 
 • May include a lesion in an anatomical location that was not scanned at baseline (i.e. brain) • Should be unequivocal and not due to differences in scanning technique • If equivocal, should be assessed at next timepoint; if present, PD is the date the lesion was first seen (not the date confirmed)
3. irRECIST Overall Tumor Assessment	
CR	
 • Complete disappearance of all measurable and nonmeasurable lesions (from baseline) and there are no unequivocal new lesions (unconfirmed CR). • Lymph nodes must decrease to < 10 mm in short axis. • Confirmation of response is required ≥ 4 weeks later, preferably at next time point, to be considered a confirmed CR.
PR	
 • If the SOD_{timepoint} of TLs decreases by $\geq 30\%$ compared to SOD_{baseline} and there are no unequivocal new lesions, and no progression of nontarget disease, it is an PR (unconfirmed). • Confirmation is required ≥ 4 weeks later, preferably at next time point, to be considered a confirmed PR.
SD	
Failure to meet criteria for CR or PR in the absence of PD.
 
 • If the sum of the TLs and the status of the nontarget lesions do not reach the criteria to meet PR or PD (increase $\geq 20\%$ and at least 5 mm absolute increase in SOD compared to nadir[†]) the response is SD. • SD = neither 30% decrease compared to SOD_{baseline} or 20% increase and at least 5 mm absolute change compared to nadir. • †SOD_{nadir}: Lowest measure SOD of TLs at any time point from baseline onward.
PD	Minimum 20% increase and a minimum 5 mm absolute increase in SOD compared to nadir, or PD for nontarget lesion(s) or unequivocal new lesion(s).

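### The irCR definition accepts target nodes under 10 mm, but the derivation table needs a 100% fall in a sum that includes those nodes, so the CR/PR split is undefined and, in uncommon sequences, so is responder status

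*Protocol*

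**What the plan says.** Protocol Appendix 1 defines irCR in two parts. The first is "Complete disappearance of all measurable and nonmeasurable lesions (from baseline"), with no unequivocal new lesions. The second is the nodal allowance, "Lymph nodes must decrease to <10 mm in SDi". SAP 13.1 carries the same limit, ending "mm in short axis".

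A nodal target must measure at least 15 "mm in short axis (SDi) for nodal lesions" at baseline. The baseline sum is "Sum of diameters at baseline = LDi of all non-nodal + SDi of all nodal target lesions". At later visits the instruction is "Measure the respective LDi and SDi for all target lesions and calculate time point SOD". A target of 5 to 10 mm is entered at its actual size, and one too small to measure is entered as 5 mm, not zero.

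The derivation table that closes both appendices classifies by the column "Target Lesions (% change in SOD"). Its only CR row needs a fall of 100 with non-target and new lesions absent. Any other fall of at least 30 without new lesions or non-target progression is PR. No footnote exempts small nodes.

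SAP 5.4, Table 4 ("General Rules Deriving BOR per irRECIST") turns visit responses into best overall response (BOR). CR then CR is CR, and PR then PR or CR is PR. CR then PR is SD, or PD if the SD lasted under 5 weeks. ORR counts only confirmed CR or PR.

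**The concern.** Investigators record each visit's response from an appendix that contains both rules, and SAP 5.4 programs BOR from those CRF responses. Two assessors who follow the appendix correctly can record different categories for the same scan. The independent readers of the endometrial and renal cohorts use the same criteria, so some disagreement in the planned concordance analysis could come from the wording rather than from the images.

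At stake first is the count of complete responses in BOR tables. Site conduct is also affected, because irCR triggers a follow-up brain scan and, except in head and neck cancer, a bone scan. There is a narrower route to the primary endpoint, because Table 4 does not treat a CR followed by PR as a confirmed response.

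**Working it through.** The plan gives no figure to reproduce here. The check applies the two rules to the same measurements.

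**1. Can a node under 10 mm ever satisfy the table?** Inputs are a nodal target of at least 15 mm at baseline and under 10 mm later, with all other lesions gone.
- Fall = 1 − (current sum / baseline sum).
- Node 15 to 9 mm: 1 − 9/15 = 40%. Definition irCR, table irPR.
- Node 15 mm to the 5 mm default: 1 − 5/15 = 66.7%. Definition irCR, table irPR.
- Limiting case: 1 − 10/15 = 33.3%. The fall always exceeds this, and non-nodal targets that vanish only increase it.

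A residual node therefore never reaches 100% and never falls short of 30%. At that visit the table always gives irPR.

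**2. When does responder status change?** Take a baseline of lung 30 mm + node 20 mm = 50 mm.

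| Scan | Lung | Node | Sum | Fall | Definition | Table |
|---|---|---|---|---|---|---|
| 1 | 0 | 9 | 9 | 1 − 9/50 = 82% | irCR | irPR |
| 2 | 0 | 10 | 10 | 1 − 10/50 = 80% | irPR | irPR |

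From nadir the sum rises by 1 mm, or 1/9 = 11%, so this is not progression. If nothing else confirms a response, Table 4 gives SD by the definition (CR then PR) and PR by the table (PR then PR).

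**3. Which sequences change?** Every ordering of CR, PR, SD, PD and NE containing at least one CR was run through Table 4 with its special cases. Each was scored once as recorded and once with each CR, taken to be nodal, recoded to PR.

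| Visits | Sequences with a CR | Status changes, any PD ends the search | Status changes, only two consecutive PDs end it |
|---|---|---|---|
| 2 | 9 | 1 | 1 |
| 3 | 61 | 8 | 9 |
| 4 | 369 | 37 | 49 |

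These are counts of patterns, not probabilities, and not every pattern need be reachable with real measurements. Every change goes the same way: non-responder by the definition, responder by the table. Changing patterns include CR-PR with nothing later to confirm, CR-SD-CR, CR-SD-PR and CR-NE-PR. CR-CR, CR-NE-CR, PR-CR, CR-PR-PR and CR-PR-CR are responders under both rules.

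**4. Size of one change.** 1/20 = 5.0 points and 1/120 = 0.8 points. With exact intervals, 6/20 has 95% CI 0.119 to 0.543 and 5/20 has 0.087 to 0.491. One responder can also decide a count rule, such as at least 3 of the first 10 or more than 12 of 60.

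**5. Size of the CR/PR effect.** The documents do not give the share of complete responders with a residual target node. As an assumption only, take 6 to 12 complete responders among 120 and a share of 20% to 50%. Then 0.2 × 6 = 1.2 to 0.5 × 12 = 6, or about 1 to 6 CRs, would be recorded as PR under the table.

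**The case against.** **The endpoints pool CR and PR.** ORR at Week 24, ORR, DCR and CBR all do so, and a CR rate alone is not a listed primary or secondary endpoint. This stands. It confines the certain effect to BOR categories and exploratory response tables.

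**A reader might infer that the primary ORR is materially wrong.** The documents do not support that. A change needs a nodal target, an otherwise complete response, and no other confirming pair. Scans at Weeks 6, 12, 18 and 24 give several chances to confirm.

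**A reader might infer that the CR rate will be understated.** That assumes assessors follow the table over the explicit nodal threshold, and the plan does not say which prevails.

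**The text might be read consistently.** One could say that disappearance means every target node must vanish, but then a 10 mm limit for target nodes would do nothing. One could read the footnote restricting decreases to measurable lesions as dropping small nodes. That conflicts with the instructions to enter 5 to 10 mm diameters and to sum all targets.

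**Aligning the table alone has a cost.** This stands. In the 9 to 10 mm example it turns a PR into SD, so the CR-then-PR row of Table 4 must be settled too.

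**Deriving irCR by program from lesion data would be a change of method.** This also stands, because BOR is built from CRF-recorded responses.

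**Conclusion.** The contradiction is real, and neither document resolves it, since SAP 13.1 repeats both the definition and the table. Read literally, the table scores every subject with a residual target node as irPR at best, whereas the definition can give irCR. That effect on the CR/PR split follows from the text alone. The figure of 1 to 6 per 120 is illustrative and rests wholly on the assumed inputs.

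For ORR the effect is conditional and probably small. Each affected subject is worth 5 points at N = 20 or 0.8 points at N = 120, always with fewer responders under the definition. The documents do not allow its frequency to be estimated. The inconsistency should be corrected, but it is no ground for calling the primary result unreliable.

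**What to change.** 1. In Protocol Appendix 1 and SAP 13.1, change the target-lesion entry of the irCR row, or add a footnote, to: all non-nodal target lesions absent and all nodal target lesions <10 mm SDi. Sites and independent readers then record the response by one rule.
2. In SAP Table 4, state how CR followed by PR is scored when the only change is a target node returning to 10 mm or more without meeting progression. Without this, step 1 makes such subjects non-responders.
3. Report a sensitivity count of responders and of complete responders under the other reading. If responses have already been recorded, state which rule was used.

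The cost is one table entry or footnote in each document, one sentence in Table 4 and one extra count from lesion diameters already on the eCRF. The small downside is that ORR in those sequences depends on the Table 4 rule chosen, which is why the sensitivity count is needed. No lesion-level re-derivation should override the investigator-recorded category.
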